Footnotes for Schedule of Activities
1. Protocol Activities: All assessments should be performed prior to dosing with study medications unless otherwise indicated. Acceptable time windows for performing each assessment are described in the column headings.
2. Lead-in PK Period: All patients in the Dose Finding Phase, and at least 8 patients in the Dose Expansion Phase.
3. End of Treatment/Withdrawal: Obtain these assessments if not completed in the prior week, except for tumor assessment which need not be repeated if performed within the prior 6 weeks.
4. Follow-up Day 28 after last dose: To occur at least 28 days, and no more than 35 days, after discontinuation of treatment. See footnote 19 and Section 8.1.1 .
5. Informed Consent: Must be obtained prior to undergoing any trial specific procedure.
6. Medical/Oncological History: To include information on prior systemic adjuvant or neoadjuvant therapy regimens, surgery and radiation therapy.
7. Baseline Signs/Symptoms: To be documented and recorded at Lead-in Day 1 or Cycle 1 Day 1 predose for all patients.
8. Physical Examination: Includes an examination of major body systems, assessment of ECOG performance status, and weight (height included at screening only).
9. In Clinic Blood pressure, pulse rate: Blood pressure, and pulse rate should be taken with the patient in the seated position after the patient has been sitting quietly for at least 5 minutes. Two blood pressure readings will be taken at least 1 hour apart at each clinic visit.
10. Home blood pressure monitoring: All patients will receive home blood pressure monitoring devices and blood pressure will be monitored at home. While on axitinib (as single agent during the Lead-in, or combined with MK-3475) patients will monitor their blood pressure at least twice daily (before taking each dose of axitinib) and blood pressure should be recorded in a patient diary. Patients should be instructed to contact the site immediately for guidance if their systolic blood pressure rises above 150 mm Hg, diastolic blood pressure rises above 100 mm Hg, or if they develop symptoms perceived to be related to elevated blood pressure (eg, headache, visual disturbance) although a different blood pressure threshold for contacting the site may be used according to the Investigator's clinical judgment (see Section 5.2.7.3 ).

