19. **Adverse Events:** Adverse events should be documented and recorded at each visit using NCI CTCAE version 4.03. For SAEs, the active reporting period to Pfizer or its designated representative begins from the time that the patient provides informed consent, which is obtained prior to the patient's participation in the study, ie, prior to undergoing any study-related procedure and/or receiving investigational product, through and including 90 calendar days after the last administration of the investigational product and before initiation of a new anti-cancer treatment. The prolonged follow up is due to the pharmacokinetic properties of the investigational product MK-3475. SAEs experienced by a patient after the active reporting period (see [Section 8.1.1](#)) has ended should be reported to the Sponsor if the Investigator becomes aware of them; at a minimum, all SAEs that the Investigator believes have at least a reasonable possibility of being related to study drug are to be reported to the Sponsor. AEs (serious and non serious) should be recorded on the Case Report Form (CRF) from the time the patient has taken at least one dose of study treatment through last patient visit (Day 28 after last dose). If a patient begins a new anticancer therapy, the AE reporting period for non serious AEs ends at the time the new treatment is started. Pregnancy or breast feeding that occur during the trial, within 120 days of discontinuing treatment with MK-3475, or within 28 days after the cessation of study treatment if the patient begins a new anticancer therapy, whichever is earlier, should be reported as in [Section 8.4 \(Exposure During Pregnancy\)](#).

20. **Concomitant Medications/Treatments:** Concomitant medications and treatments will be recorded from 28 days prior to the start of study treatment and up to 28 days after the last dose of study treatment. All concomitant medications should be recorded in the CRF including supportive care drugs (eg, anti-emetic treatment and prophylaxis), and the drugs used to treat adverse events or chronic diseases, and non-drug supportive interventions (eg, transfusions).

21. **Registration:** Patient number and dose level allocation operated by Pfizer Inc. Required information: site and patient identifiers and demographic information. Study treatment (either single agent axitinib for patients in Lead-in or axitinib in combination with MK-3475 for all other patients) should begin within 7 days of registration.

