#### **8.1.4.1. Reporting SAEs to Pfizer Safety**

All SAEs occurring in a patient during the active collection period are reported to Pfizer Safety on the CT SAE Report Form.

SAEs occurring in a patient after the active collection period has ended are reported to Pfizer Safety if the investigator becomes aware of them; at a minimum, all SAEs that the investigator believes have at least a reasonable possibility of being related to investigational product must be reported to Pfizer Safety.

Follow up by the investigator continues throughout and after the active collection period and until the event or its sequelae resolve or stabilize at a level acceptable to the investigator, and Pfizer concurs with that assessment.

- If a patient begins a new anticancer therapy, SAEs occurring during the above indicated active collection period must still be reported to Pfizer Safety irrespective of any intervening treatment.

Pregnancy or breast feeding that occur during the trial, within 120 days of discontinuing treatment with MK-3475, or within 28 days after the cessation of study treatment if the patient begins a new anticancer therapy, whichever is earlier, should be reported as in [Section 8.4](#) (Exposure During Pregnancy).

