#### **8.1.4.2. Recording Non-serious AEs and SAEs on the CRF**

During the active collection period, both non serious AEs and SAEs are recorded on the CRF.

Follow up by the investigator may be required until the event or its sequelae resolve or stabilize at a level acceptable to the investigator, and Pfizer concurs with that assessment.

If a patient begins a new anticancer therapy, the recording period for non serious AEs ends at the time the new treatment is started; however, SAEs must continue to be recorded on the CRF during the above indicated active collection period.

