## Appendix 6. Revised Schedule of Activities Following Collection of Data for Primary Study Objective

After the collection of data for the primary study objective and most of the secondary objectives has been completed, patients who are still clinically benefiting from study treatment as judged by the investigator may be candidates for continuation of study treatment. Discussion with sponsor is required.

The following protocol sections should be disregarded: [Schedule of Activities](#) the original protocol and the trial procedures in [Section 6.2](#) Study Period, [7.2](#) Pharmacokinetics Assessments, [7.2.1](#) Blood Sample Collection for Pharmacokinetic Analysis, [7.2.2](#) Collection of Axitinib PK Samples, [7.2.3](#) Processing, Storage and Shipment of Axitinib PK Samples, [7.2.4](#) Collection and Processing of MK-3475 PK Samples, [7.2.5](#) Collection and processing of anti-MK3475 Antibody Samples, and [7.3](#) Translational and Pharmacodynamic Assessments. The investigator may schedule visits (unplanned visits) in addition to those listed in the [Schedule of Activities](#) table in order to conduct evaluations or assessments required to protect the well-being of the patient.

The following schedule of activities will be implemented for patients still on active treatment and long-term survival follow-up. Patients on axitinib monotherapy have the opportunity to continue axitinib treatment on a Pfizer-sponsored patient access program at the time of the discontinuation of survival status follow-up.

Protocol Activities and Forms to be Completed	Study Treatment 	Post-Treatment		
	Cycles ≥24 Day 1 -3/+3	End of Tx or Withdrawal  -3/+3	28 Days Post-Treatment -7/+7	Survival Follow-Up -7/+7
Physical Examination 	X	X		
In Clinic Blood Pressure, Pulse Rate 	X	X		
Home Blood Pressure Monitoring 	X	X		
Hematology 	Local Standard of Care	X		
Blood Chemistry 	Local Standard of Care	X		
Coagulation 	Local Standard of Care			
Urinalysis 	X			
12-lead ECG 	X	X		
Thyroid Function Tests 	X	X		
Pregnancy Test 	X	X		
Tumor Assessments 	Local Standard of Care and at End of Treatment			
Adverse Events 	X	X	X	
Concomitant Medications/Treatments 	X	X	X	
Study Treatment 	X			
Post Study Survival Status 			X	X

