12. Adverse Events: Adverse events should be documented and recorded at each visit using NCI CTCAE version 4.03. For SAEs, the active reporting period to Pfizer or its designated representative begins from the time that the patient provides informed consent, which is obtained prior to the patient's participation in the study, ie, prior to undergoing any study related procedure and/or receiving investigational product, through and including 90 calendar days after the last administration of the investigational product and before initiation of a new anti-cancer treatment. The prolonged follow up is due to the pharmacokinetic properties of the investigational product MK-3475. SAEs experienced by a patient after the active reporting period (see Section 8.1.4 ) has ended should be reported to the Sponsor if the Investigator becomes aware of them; at a minimum, all SAEs that the Investigator believes have at least a reasonable possibility of being related to study drug are to be reported to the Sponsor. AEs (serious and non serious) should be recorded on the Case Report Form (CRF) from the time the patient has taken at least one dose of study treatment through last patient visit (Day 28 after last dose). If a patient begins a new anticancer therapy, the AE reporting period for non serious AEs ends at the time the new treatment is started. Pregnancy or breast feeding that occur during the trial, within 120 days of discontinuing treatment with MK-3475, or within 28 days after the cessation of axitinib if the patient begins a new anticancer therapy, whichever is earlier, should be reported as in Section 8.4.2.1 (Exposure During

Pregnancy).
13. Concomitant medications and treatments will be recorded from 28 days prior to the start of study treatment and up to 28 days after the last dose of study treatment. All concomitant medications should be recorded in the CRF including supportive care drugs (eg, anti emetic treatment and prophylaxis), and the drugs used to treat adverse events or chronic diseases, and non-drug supportive interventions (eg, transfusions).

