6.2.2. Adverse Events

AEs will be characterized by type, frequency, severity (as graded by NCI CTCAE version 4.03), timing, seriousness and relationship to study treatment. Adverse events occurring during the 7 day lead in phase for PK will be summarized separately from adverse events reporting after first dose of MK-3475 (C1D1). Baseline signs and symptoms will be recorded at baseline and then reported as adverse events during the trial if they worsen in severity or increase in frequency.

Treatment Emergent Adverse Events

All deaths and serious AEs, regardless of cause, occurring from start of treatment until 28 days after the last dose will be considered treatment-emergent. All other non-serious AEs occurring after treatment start regardless of cause, will be considered treatment-emergent up until 28 days after the last dose or until start of new anti-cancer treatment, whichever occurs first. Disease progression is not considered a treatment emergent AE unless the patient dies of disease prior to 28 days after the last dose. Events that are continuations of baseline abnormalities are considered treatment emergent AEs only if there is an increase in grade over baseline, or if there is an increase following a decrease during the study.

For subjects with a 7 day lead-in phase for PK, adverse events reported during the lead-in phase will only be considered as treatment emergent for the combination if there is an increase in grade after the first dose of MK-3475 (C1D1) or if there is a decrease and then subsequent increase during treatment with the combination.

Treatment Related Adverse Events

Treatment emergent AEs with causality related to treatment, as judged by the investigator, will be considered treatment-related. Events that are continuation of baseline abnormalities are not considered treatment- related unless there is an increase in grade, or if there is an increase following a decrease, and the increase is judged by the investigator to be due to treatment.

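### The Schedule footnotes end active SAE reporting when a new anti-cancer treatment starts, while Section 8.1.4 keeps it running to at least day 90

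*Protocol*

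**What the plan says.** **Footnotes.** Footnote 19 of the Schedule of Activities defines active SAE reporting to the sponsor as running from consent "through and including 90 calendar days after the last administration of the investigational product and before initiation of a new anti-cancer treatment". It attributes the long follow-up to the pharmacokinetics of MK-3475. Appendix 6 footnote 12, which serves the reduced schedule for continuing patients, sets the same limit: "90 calendar days after the last administration of the investigational product and before initiation of a new anti-cancer treatment".

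Both footnotes contain two further rules:
- SAEs arising after the active period "has ended should be reported to the Sponsor if the Investigator becomes aware of them", and at a minimum those the investigator considers possibly related.
- Serious and non-serious AEs go on the CRF up to the last patient visit, which the footnotes identify as Day 28 after the last dose. A new anti-cancer therapy cuts this short for non-serious AEs only.

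**Section 8.** Section 8.1.4 runs the active collection period to at least 90 days after the last dose and does not stop it at new therapy. Section 8.1.4.1 states: "SAEs occurring during the above indicated active collection period must still be reported to Pfizer Safety irrespective of any intervening treatment". Section 8.1.4.2 ends recording of non-serious AEs at new therapy, but "SAEs must continue to be recorded on the CRF during the above indicated active collection period".

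**Analysis.** Protocol Section 9.6 extends the safety analysis through 90 days after the last dose. SAP 6.2.2 uses a shorter window: "All deaths and serious AEs, regardless of cause, occurring from start of treatment until 28 days after the last dose will be considered treatment-emergent".

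**Visit timing.** Footnote 4 places the follow-up visit as follows: "To occur at least 28 days, and no more than 35 days, after discontinuation of treatment". The Appendix 6 column heading is "28 Days Post-Treatment -7/+7".

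**The concern.** The Schedule is the page that sites work from, and for continuing patients Appendix 6 replaces the main Schedule. Appendix 6 lists the protocol sections to disregard. Section 8.1.4 is not among them, and footnote 12 cites it for the very period that the footnote then shortens. Footnote 19 cites Section 8.1.1, which covers CRF terminology and defines no period.

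The protocol explains why the 90 days matter: MK-3475 persists, and Section 5.2.7.4 says that immune-related events can appear several months after the last dose. If active reporting ends at the next therapy, the SAEs that are actively sought depend on when that therapy starts and on which passage the site follows. The passive fallback has little behind it, since the Appendix 6 schedule marks no AE assessment under survival follow-up. At stake are timely safety reporting to the sponsor and the completeness of SAE data after Day 28.

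**Working it through.** The plan gives no figure to reproduce. The check sets the rules side by side, counts days after the last dose, and lets new therapy start on day d.

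| SAE rule | Footnotes 19 and 12 | Sections 8.1.4 to 8.1.4.2 |
|---|---|---|
| Active reporting to the sponsor ends | day d, or day 90 without new therapy | day 90 at the earliest |
| After that | reported if the investigator becomes aware | reported if the investigator becomes aware |
| CRF recording of SAEs ends | Day 28, whatever d is | day 90 at the earliest |
| Effect of new therapy on CRF recording | non-serious AEs only | non-serious AEs only |

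The analysis windows are Day 28 for treatment-emergent SAEs (SAP 6.2.2, regardless of new therapy) and day 90 for safety overall (protocol 9.6).

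**Step 1. Active reporting closed by new therapy.** Days closed = 90 − d. The values of d are assumed.
- d = 7: 90 − 7 = 83 days
- d = 14: 90 − 14 = 76 days
- d = 21: 90 − 21 = 69 days (69/90 = 77%)
- d = 28: 90 − 28 = 62 days
- d = 60: 90 − 60 = 30 days

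**Step 2. SAP window closed by new therapy.** SAP 6.2.2 counts SAEs to Day 28. The footnotes keep SAEs on the CRF to Day 28 for every d. Days closed = 28 − 28 = 0.

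**Step 3. CRF gap after Day 28.** Against Sections 8.1.4.2 and 9.6, the footnotes leave 90 − 28 = 62 days (days 29 to 90) without required CRF recording of SAEs. This does not depend on d.

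**Step 4. The two gaps together.** With d = 21, an SAE on days 22 to 28 (7 days) is on the CRF but not actively reported. On days 29 to 90 (62 days) it is neither actively reported nor required on the CRF. The sum, 7 + 62 = 69, agrees with step 1. With no new therapy, an SAE on days 29 to 90 is still actively reported to the sponsor, but the footnotes do not require it on the CRF.

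**Step 5. Visit window.** Appendix 6 permits the visit from day 28 − 7 = 21 to day 28 + 7 = 35, while footnote 4 permits days 28 to 35. If a site treats a day-21 visit as the end of recording, days 22 to 28 are missed: 7 of 28 days (25%). If it reads Day 28 as the fixed limit, none are missed.

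**The case against.** The strongest reply is that the footnotes hold two separate rules and only one is in conflict. The new-therapy clause governs active reporting to the sponsor. The CRF sentence keeps serious AEs to Day 28 and matches SAP 6.2.2 exactly. Nor does reporting cease altogether, because SAEs that come to the investigator's attention are still reported. The SAP also summarises deaths separately, within and beyond 90 days of the end of treatment, and survival follow-up continues. The documents give no switching times, so any value of d is hypothetical.

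Most of this stands, and it limits the point. A reader might infer that a site following the Schedule loses SAEs that the SAP counts as treatment-emergent, or that SAE incidence is therefore biased downward. The documents do not support either inference: step 2 gives 0 days for any d, and no bias in the treatment-emergent summaries follows from new therapy. A reader might also infer that the footnotes stop SAE reporting. They end only the active period.

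The reply does not remove the contradiction. Passive reporting is weaker than the duty in Section 8.1.4.1, and the instructions differ for every SAE between new therapy and day 90. Nor does it answer the Day 28 CRF limit, which conflicts with Sections 8.1.4.2 and 9.6 for every patient.

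The visit-window point is secondary. It concerns only patients on the reduced schedule and depends on how the footnote is read.

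**Conclusion.** The contradiction is real and should be reconciled. Under the footnotes, new therapy on day d closes 90 − d days of mandatory active SAE reporting that Section 8.1.4 requires: from 83 days at d = 7 to 30 days at d = 60. How many SAEs this involves is unknown, because the documents give neither the frequency nor the timing of early switching.

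New therapy removes nothing from the SAP's 28-day SAE window. The effect on analysis data comes from the separate Day 28 CRF limit. SAEs on days 29 to 90 may be understated in a safety analysis that Section 9.6 carries to day 90. They may also be understated in the SAP's SAE listing, which is not explicitly restricted to treatment-emergent events. This holds with or without new therapy.

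**What to change.** 1. In footnote 19 and Appendix 6 footnote 12, delete from the SAE sentence the closing clause that ends the period at a new anti-cancer treatment. Keep the new-therapy stop for non-serious AEs only.
2. In both footnotes, reconcile the Day 28 end of CRF recording for SAEs with Sections 8.1.4.2 and 9.6. Step 1 alone would leave this gap open.
3. Correct the cross-reference in footnote 19 from Section 8.1.1 to Section 8.1.4. Footnote 4 carries the same reference.
4. As a minor point, reconcile the Appendix 6 visit window with footnote 4, or state that AE recording runs to Day 28 whatever the visit date.
5. While editing, confirm that the new-therapy cut-off for Events of Clinical Interest in Section 7.1.2.1 is intended, since those events can be serious.

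The cost is a few text edits by amendment or site letter, plus some SAE reports and CRF entries that Section 8.1.4 already requires.

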## SCHEDULE FOR PHARMACOKINETIC SAMPLE COLLECTION

Axitinib		Axitinib in Combination with MK-3475						
Lead-in Day7	Cycle 1			Cycles 3 and 5		Cycle 7	Cycle 11 and every 12 weeks thereafter	
	Day 1		Day 5	Day 1		Day 1	Day 1	
PK Samples for axitinib a	PK Samples for MK-3475 b	Sample for anti-MK-3475-antibodies (ADA) c	PK Sample for MK-3475 b	PK Sample for MK-3475 b	Sample for anti-MK-3475-antibodies (ADA) c	PK Samples for axitinib a	PK Sample for MK-3475 b	Sample for anti-MK-3475-antibodies (ADA) c
Prior to axitinib morning dose	Prior to MK-3475 dose	Prior to MK-3475 dose	One sample collected at any time between Cycle 1 Day 3 and Cycle 1 Day 7 for MK-3475; the exact time/day of sample collection to be noted in Case Report Form.	Prior to MK-3475 dose	Prior to MK-3475 dose c	Prior to axitinib morning dose	Prior to MK-3475 dose	Prior to MK-3475 dose
1 hr post axitinib morning dose	End of MK-3475 infusion d					1 hr post axitinib morning dose		
2 hrs post axitinib morning dose						2 hrs post axitinib morning dose		
3 hrs post axitinib morning dose						3 hrs post axitinib morning dose		
4 hrs post axitinib morning dose						4 hrs post axitinib morning dose		
6 hrs post axitinib morning dose						6 hrs post axitinib morning dose		
8 hrs post axitinib morning dose						8 hrs post axitinib morning dose		

K= pharmacokinetics; ADA= anti-drug antibodies

Note that PK samples for MK-3475 and anti-MK-3475-antibodies (ADA) will be collected from all patients in the study. Axitinib PK samples will be collected from all patients in the Dose Finding phase and at least 8 patients in the Dose Expansion Phase.

- One sample (3 mL) collected at each time point for axitinib.
- One sample (3 mL) collected at each time point for MK-3475. Additionally PK samples will be collected at 1 month, 3 months and 6 months after end of MK-3475 treatment.
- One sample (6 mL) collected at each time point for MK-3475-antibodies.
- Sample may be collected within 30 minutes after end of MK-3475 infusion.

## 1. INTRODUCTION

### 1.1. Indication

Advanced RCC tumors in the first-line setting.

### 1.2. Background and Rationale

#### 1.2.1. Renal Cell Cancer

An estimated 65,150 new cases of kidney cancer are expected to be diagnosed in the United States (US) in 2013. This includes 93% RCC, 6% renal pelvis cancer and 1% Wilms tumor. An estimated 13,680 patients will die from kidney cancer in 2013.

RCC arises from the renal epithelium and 5 major subtypes are currently recognized. Approximately 70-80% of these are clear cell RCC tumors while other less common cell types include papillary (Type I and II), chromophobe, collecting duct and unclassified RCC. Four RCC predisposing genes have been identified – *MET* protooncogene, von Hippel-Lindau tumor suppressor gene (*VHL*), fumarate hydratase tumor suppressor gene (*FH*), and Birt-Hogg-Dubé tumor suppressor gene (*BHD*).

Patients with von Hippel-Lindau disease have a >70% risk of developing clear cell RCC. This hereditary form of RCC is caused by germline mutations in the *VHL* tumor suppressor gene on chromosome 3p. More than 90% of sporadic clear cell RCC involves somatic *VHL* gene mutations or methylation. *VHL* gene mutations lead to loss of function of the VHL protein, accumulation of hypoxia-inducible transcription factors (eg, HIF-1alpha and HIF-2 alpha) which translocate to the nucleus and increase transcription of angiogenesis factors (such as VEGF and platelet derived growth factor [PDGF]) which induce tumorigenesis. Clear cell RCC is a highly vascular tumor with high expression of VEGF, VEGFRs and PDGF receptor.

About one-third of patients with clear cell RCC present with Stage IV disease. Systemic therapy is given to patients with advanced disease (relapsed or Stage IV) that is not amenable to complete resection. However, it is recommended that these patients undergo a cytoreductive nephrectomy where possible, prior to beginning systemic therapy, as per treatment guidelines.

There are 7 molecularly targeted agents approved in the US as systemic therapy for advanced RCC that is predominantly clear cell. First line systemic therapy is usually one of the VEGFR TKIs (sunitinib, pazopanib, or sorafenib), the monoclonal anti-VEGF antibody bevacizumab (given in combination with IFN alpha) or the mTOR inhibitor, temsirolimus. The same targeted agents or the VEGFR TKI axitinib, or the mTOR inhibitor everolimus are used individually in subsequent lines of therapy for advanced clear cell RCC.

